## 5. Recruitment of study participants

---

All adults and adolescents aged 16 years or older (age of consent for HIV testing in Zambia) accessing HTS in clinics where HIVST distribution is being implemented are eligible for participation.

Specifically, individuals will be eligible to participate in data collection for the case studies if they:

- Are aged 16 years or older, and
- Able and willing to provide informed consent.

An individual is not eligible for participation in the study if they are:

- Under 16 years of age
- Unable and unwilling to provide informed consent
- Individuals not offered an HIVST kit, or
- If there is anything that, in the opinion of the investigator, would preclude informed consent or make study participation unsafe.

For the secondary distribution cohorts, participants are eligible if they meet these criteria and they are attending ANC or HIV testing and treatment services where secondary distribution of test kits is being offered. Informed consent will be sought for an exit interview and individuals who report accepting an offer of HIVST for secondary distribution to a partner will be eligible for a follow-up interview. Partners (intended users) of index individuals who collect an HIVST for secondary distribution will also be eligible for follow-up, providing consent is gained from the index individual at their follow-up interview and from the intended user.

### 5.1 Recruitment of qualitative study participants

In total 46 IDIs, 12 FGDs, 4 stakeholder meetings and 15 observations will be conducted. The 42 IDIs will be conducted with purposefully selected individuals accessing VMMC (6), facility/ community-led (6), work places (6) ANC (12) HIV+ individuals (12) and health care workers (4). The 12 FGDs will be conducted with purposely selected community members to obtain community perspectives on the different models; 4 for the ANC model, 4 for HIV+ individuals' model, 1 for VMMC model, 2 for facility-led/community-led model and 1 for the workplace model. Of the 4 FGDs for the ANC model, 2 will be composed of individuals attending the ANC at the clinic and the other 2 of ordinary community members (women) recruited from the community. Similarly, the 4 FGDs for HIV+ will be divided into 2 (mixed sex) for individuals attending ART recruited from the clinic and the other 2 ordinary community members (mixed sex) recruited from the community. The VMMC and work place FGDs will be composed of individuals about to undergo VMMC and staff of work place. Stakeholder meetings will be conducted with representatives of different groups identified during community consultations. The four HCWs who are involved in distributing HIVST will be purposely selected (to ensure a

mix of gender and type or aspect of the model they are involved in) to take part in qualitative interviews. They will be asked for their perspectives on HIVST and the distribution models, linkage to care and prevention services, social harms and sustainability of the models. The study will be explained to them and consent obtained before taking part in the study. Other HCWs may take part in stakeholder meetings at the beginning of the study if the clinic/ HCWs are identified as key stakeholders in HIV care and prevention activities in the community.

Recruitment of participants for the qualitative enquiry will be conducted at 1) the point of distribution/clinic and 2) in the community. Individuals who come to access HTS at the HIVST distribution points will be approached to consent for participation in IDIs and FGDs. Community members who have not yet accessed HIVST or have accessed but have not been selected as IDI participants will be approached to participate in FGDs. Selection of the community members who have not yet accessed HIVST will be done in consultation with existing adolescent community advisory boards, adult community advisory boards, neighbourhood health committees and other community-based stakeholders identified during the community consultation process. These participants will be selected because they are information rich participants who will make meaningful contributions to the interviews/ discussions

Community-based mechanisms for identifying, documenting, and mitigating social harms will be implemented in all models, except the two secondary distribution models in ANC and HIV+ individuals. However, qualitative research participants in the two secondary distribution models will be interviewed for social harms and observation will be made in the qualitative cohort participants (see recruitment details below). The type and nature of the mechanisms will depend on the recommendations from the consultation process. The consultations may recommend use of existing community-based structure (s) or creation of a new one (s). If creation of new structures is recommended, selection of members will be done using criteria developed from the consultative process.

Recruitment of qualitative participants in the workplace model will be done during the distribution process. The SFH distributors will explain to the workers about the need to evaluate HIVST distribution in workplaces. Individuals will then be asked if they are willing to take part in such a research activity. Individuals willing to participate in the workplace research activities will be asked for their name and contact number and for verbal permission to share this information with the researchers. The RAs with the help of a senior social scientist will contact the individuals through phone calls to set up interview appointments. Participants will suggest places where they will be comfortable to be interviewed from. Where possible space for interviews will be provided within the work place to provide a choice to participants. Written informed consent will be obtained from participants and the interview will last between 30 to 45 minutes.

## **5.2 Recruitment of secondary distribution cohorts**

For the secondary distribution cohorts, consecutive study participants will be recruited as they exit their clinical consultation at ANC or HIV testing and treatment services. The staff in charge of HIVST distribution will refer all individual who are offered an HIVST for secondary

distribution. Willing potential study participants will then be referred to Zambart Research Assistants (RAs). To facilitate good rapport between research staff and clinic attendees, the staff in charge of HIVST distribution will introduce the individuals to the study RA.

After introductions, the study RAs will provide detailed information about the study and request written informed consent. They will then administer an “exit” interview. The exit interview will include socio demographic factors, history of HIV testing, and their partners’ history of HIV testing, details about their relationship with their partner including questions about gender based violence and whether they were offered a secondary distribution HIVST. If they were offered secondary distribution HIVST they will be asked whether they accepted or declined the offer of a secondary distribution HIVST and the reasons influencing their decision.

After completion of the exit interview, individuals reporting that they accepted the HIVST for secondary distribution will be asked for their consent to be followed-up as they come back for their clinical appointment or at home within 1-month of the “exit” interview to participate in a follow-up interview. To facilitate follow-up of cohort participants and individuals who will be selected to participate in qualitative activities, RAs will obtain locator information from consenting individuals, including telephone numbers and home address.

Approximately one-month after the offer of HIVST for secondary distribution, RAs will follow-up cohort participants who reported accepting an offer of an HIVST for secondary distribution, either at the health facility or in their homes or other convenient place. It is anticipated that a number of individuals who will accept the offer of HIVST secondary distribution may not return to the clinic on the appointment day for various reasons. Such individuals will be followed-up using a phone call or to their homes using the information provided during the exit interviews. A maximum of three (3) attempts on three different days through phone calls or home visit will be made. Individuals not answering the phone calls or not at home after three attempts will be considered lost-to-follow-up from the cohort.

To recruit the intended users of secondary distribution HIVST, individuals accepting a secondary distribution HIVST and who report that their partner (intended user) used the HIVST will be asked for permission to contact their partners, the intended users. For individuals who will give permission, the RA will either: (1) give the individual a card containing the RA’s contact details for the partner to call the RA or (2) ask the individual if they are willing to call their partner (intended user) to ask for permission to a) share their (intended user’s) phone number with the RA b) to introduce the RA to them (intended user). For intended users who will be willing to share their phone numbers or to talk to the RA, the RA will briefly introduce the study and obtain verbal permission. For intended users who will give verbal permission, the RA will obtain contact details and arrange to meet them. A maximum of three (3) attempts on three different days through phone calls will be made to contact or meet the intended user. RAs will arrange to meet the intended user at the clinic or at their home or any place provided it is safe and convenient for both the RA and the intended user. The intended user will also be provided with information about the study and asked to provide written consent before they are interviewed. The follow-up surveys for the distributor of the secondary distribution HIVST

and the intended user of the HIVST will focus on usage of the collected HIVST and linkage to care or HIV prevention services including their costs of accessing HIVST and linkage to HIV services as well as their willingness to pay for HIVST.

Twelve individuals (6 from the ANC and 6 from HIV+ individuals) recruited in the secondary distribution cohort will be purposively selected to participate in the qualitative cohort to explore the contextual factors affecting secondary distribution HIVST in ANC and through HIV-positive individuals. Individuals selected to participate in the cohort must have self-tested, and accepted secondary distribution on behalf of their partner. Using purposeful sampling, age, and gender will be taken into account to ensure a fair distribution of participants. Qualitative research assistants will spend extended times in the homes of the participants, using the rapport created to generate detailed data on participants' experiences with HIVST and particular the secondary distribution models. Such an ethnographic approach does not necessarily require many participants. RAs will inform quantitative cohort participants that they may be approached by researchers conducting qualitative research and asked to enrol in a qualitative cohort and that they will be asked to consent for this activity. Qualitative RAs will then approach the 12 individuals selected for the qualitative cohort and schedule interviews with them within 5 days. Follow-up interviews will be conducted immediately after the follow up visit for the quantitative cohort interviews. A key aspect of the qualitative cohort will be the extended contact with participants by the researchers in the participants' preferred milieu while at the same time conducting participatory research activities. The rapport created will be critical for prompting participants to share their experiences.

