### **4.3. Quantitative methods**

#### **4.3.1 Process data**

Process data collected during distribution of HIVST kits by the SFH and Zambart distributors will be used. SFH has developed simple tools (Appendix 2) that distributors will use for all the distribution models. The information to be collected include age, sex, level of education, occupation, whether an individual accepts the test kit or not and the reasons for not accepting the test kit. In all the distribution models, this information will be collected using a simple paper-based questionnaire or register. The process measures collected for each of the five distribution models will include:

[figure not shown]
- 1) The number of HIVST kits offered through the five models of distribution, the number of HIVST kits accepted and the number of HIVST kits returned.
- 2) Proportion of individuals offered an HIVST who accept the offer, by model of distribution

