#### **4.3.2 Secondary Distribution Cohorts**

For the two secondary distribution models, we will recruit two cohorts of individuals (one from ANC and one from HIV+ individuals attending HIV testing and treatment services) to collect data on outcomes of distribution over time (Figure 2 and 3 First, we will conduct an exit interview with consecutive HIV+ individuals (attending HIV testing and treatment services) and ANC attendees (HIV status irrelevant) to determine the proportion who accepted an offer of an HIVST for secondary distribution and determine factors associated with accepting an offer of HIVST for secondary distribution.

At the end of the exit questionnaire, individuals self-reporting that they accepted an offer of secondary distribution HIVST will be asked for permission to be followed-up within 1-month after the exit interview to measure use of the secondary distribution HIVST. We will also aim to

follow-up the intended user of the secondary distribution HIVST within approximately 3-months to measure self-reported use and linkage to care as reported by the intended users. A timeline specific to the secondary distribution cohorts is given in Figure 2.

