**Figure 2: Schematic of the quantitative and qualitative cohort in ANC and ART models**

For the secondary distribution cohorts, we will measure individual- and couple-level factors associated with acceptability to the index patient and intended user including: sex, age, previous HIV testing history, newly diagnosed or previously undisclosed HIV, relationship of the distributor and intended user (including type of relationship, age differential, measures of equality and empowerment), history of gender based violence and clinic from which the Index was recruited (ANC or HIV testing and treatment services).

The primary outcome of the secondary distribution cohorts is the:

- 1) Proportion of index patients who accepted an offer of secondary distribution HIVST kit(s) who report that their sexual partner(s) used the HIVST kit,

Secondary outcomes are the:

- 1) Proportion of index patients accepting an offer of HIVST kit(s) for secondary distribution,
- 2) Proportion of index patients who accepted an offer of a secondary distribution HIVST kit(s) who report that their partner used the HIVST kit(s) and linked to prevention or care services within 1-month of distribution

- 3) Proportion of intended recipients who self-report a) having used an HIVST kit and b) having attended confirmatory HIV testing, or HIV prevention or HIV care services within 3-months of distribution.

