### **7.3 Quantitative secondary distribution cohort data**

For the quantitative data arising from the secondary distribution cohorts, we will conduct analyses separately for the ANC and HIV testing and treatment cohorts. We will use descriptive analyses to describe the proportion of individuals accepting an offer of HIVST and the proportion who report that their partner used the HIVST. We will use standard logistic regression adjusting for study site to explore factors associated with accepting an offer of HIVST and with reported use of the HIVST.

Although the index individuals will be asked about linkage to care at 1-month follow-up, we will measure linkage to care using data from the intended users followed-up within 3-months after distribution. Linkage will be measured as the number of individuals reported to have linked to care (defined as accessing confirmatory testing services or attending an HIV care clinic for HIV-positive individuals or accessing VMMC services for HIV-negative males) among those who reported use of the HIVST.

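### The cohort acceptance proportion comes from willing, consenting interviewees and may be biased; the planned register-based figure has the right denominator but is not named as the result

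*Protocol*

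**What the plan says.** **Outcome and source.** The secondary outcomes in protocol section 4.3.2 begin with "Proportion of index patients accepting an offer of HIVST kit(s) for secondary distribution". The same section gives the exit interview the task "to determine the proportion who accepted an offer of an HIVST for secondary distribution and determine factors associated with accepting an offer". Section 7.3, on the cohort data, says the analysis will "describe the proportion of individuals accepting an offer of HIVST and the proportion who report that their partner used the HIVST".

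**Who reaches the interview.** Section 5.2 describes three steps:
- Referral: "The staff in charge of HIVST distribution will refer all individual who are offered an HIVST for secondary" distribution.
- Willingness: "Willing potential study participants will then be referred to Zambart Research Assistants (RAs").
- Consent: after an introduction by the distribution staff, "the study RAs will provide detailed information about the study and request written informed consent".

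**When interviewing stops.** Under section 5.4, exit interviews continue until about 450 clients per cohort have accepted a kit and agreed to follow-up.

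**The other source.** Section 4.3.1 lists a process measure taken from the distributors' records: "Proportion of individuals offered an HIVST who accept the offer, by model of distribution". Section 7.2 plans its descriptive analysis by age and model, with reasons for refusal. The ART and MCH secondary distribution registers in Appendix 6 have fields for facility, date, age, sex, acceptance yes or no, and reason for not accepting.

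**The concern.** The outcome is defined over clients offered a kit, but the exit interview observes only those who were willing to be referred and then signed consent. If accepters and decliners differ in willingness, the interview-based proportion does not estimate the stated quantity.

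Several features make lower willingness among decliners plausible. The staff who offer the kits operate the first filter and make the introduction. The recruitment target counts only accepters. The interview also asks about the relationship and partner violence, which a client who has just declined may not wish to discuss.

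Models 4 and 5 will thus have two acceptance proportions with different denominators. The protocol neither says which one is the result nor plans a comparison. Since the study is meant to inform scale-up and guidelines (section 2.1), readers are likely to use the acceptance figure as a measure of reach.

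**Working it through.** **No figure to reproduce.** The protocol states no expected acceptance and no interview participation rate. All values of A, wa and wd below are assumptions.

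**Formula.** Let A be true acceptance among all clients offered a kit, and wa and wd the shares of accepters and decliners who end up interviewed.

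Observed acceptance = A·wa / (A·wa + (1 − A)·wd)

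Equivalently, observed odds = true odds × (wa/wd).

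**Results at A = 75%:**

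| wa | wd | Calculation | Observed | Difference (points) |
|---|---|---|---|---|
| 0.9 | 0.9 | 0.675/(0.675 + 0.225) | 75.0% | 0 |
| 0.9 | 0.7 | 0.675/(0.675 + 0.175) | 79.4% | +4.4 |
| 0.9 | 0.5 | 0.675/(0.675 + 0.125) | 84.4% | +9.4 |
| 0.9 | 0.3 | 0.675/(0.675 + 0.075) | 90.0% | +15.0 |
| 0.7 | 0.9 | 0.525/(0.525 + 0.225) | 70.0% | −5.0 |

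**Sensitivity to A.** With wa = 0.9 and wd = 0.5:
- A = 60%: 0.54/(0.54 + 0.20) = 73.0%, or +13.0 points.
- A = 90%: 0.81/(0.81 + 0.05) = 94.2%, or +4.2 points.

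With wa = 0.9, wd from 0.7 to 0.3 and A from 60% to 90%, the difference runs from about +2 to +22 points. With wa = 0.7 and wd = 0.9 it runs from −2.5 to −6.2.

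**Comparison with sampling error.** About 450 accepters at 75% acceptance implies roughly 450/0.75 = 600 interviews. The 95% half-width is 1.96 × √(0.75 × 0.25/600) = 3.5 points. The same calculation gives 3.5 points at 60% (750 interviews) and 2.6 at 90% (500 interviews). At 75%, even the mildest unequal case in the table (+4.4) exceeds it, and a larger sample would not reduce the error.

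**Associated factors.** If willingness depends only on acceptance, wa/wd is the same at every level of a factor and cancels from the odds ratio. The logistic regression for objective 9 is then much less exposed than the proportion.

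**With the register as source.** If everyone offered a kit is recorded, the interview-selection term drops out and observed acceptance equals A.

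**The case against.** The strongest reply is that the protocol already covers this. Sections 4.3.1 and 7.2 plan the acceptance proportion from process data for every model, with reasons for refusal. Objective 1 describes distribution, while objective 9 concerns factors associated with acceptance. That stands: the register figure is a planned output, and a reader who inferred that the registers go unused for acceptance would be wrong. What remains is that section 4.3.2 attaches the named outcome to the interview and leaves the relation between the two figures unstated.

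Second, recruitment is consecutive, staff are told to refer everyone offered a kit, section 3 has researchers meeting people whether or not they accept, and the exit form records consent yes or no. These steps limit selection. But the willingness step comes before the research assistant, and no tool in the appendices counts clients lost there.

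Third, a reader might infer that acceptance will be overstated. The documents do not support that as fact, because they give no willingness by acceptance status. Equal willingness gives no bias, and greater willingness among decliners reverses its sign.

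Fourth, the registers have weaknesses of their own. Completeness for decliners is not stated. Appendix 1 promises recognition to high-performing facilities, so under-recording of refusals could bias that figure upward too. Appendix 1 also offers kits in postnatal clinics, whereas the cohort is of ANC attendees, and the register is headed MCH. Section 6.2 keeps identifiers out of the process database, so individual linkage is not provided for. All of this stands and limits the remedy.

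**Conclusion.** The point holds in limited form. Secondary outcome 1 is assigned to a source whose denominator is narrower than its definition, and the protocol does not say whether the interview or register figure is the result for models 4 and 5. The interview figure may be biased, plausibly upward, but neither direction nor size can be established from the documents. The calculated range rests wholly on the assumed acceptance and willingness; it shows only that moderate differences in willingness could exceed sampling error.

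One descriptive secondary outcome is affected. The primary outcome, partner use among accepters, does not use this denominator, and the sample size in section 5.4 does not depend on it. The point is minor to moderate.

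**What to change.** In sections 4.3.2 and 7.3:

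1. Take the proportion for secondary outcome 1 from the ANC/MCH and ART secondary distribution registers: accepted divided by all offered, in the same clinics and recruitment dates. For the ANC cohort, count ANC clients only. The trimester column of the MCH register may help to separate them from postnatal clients.
2. Keep the exit interview for factors associated with acceptance (objective 9).
3. Report the interview-based proportion beside the register figure, with aggregate counts of clients offered and interviewed by acceptance, age and sex. No individual linkage is needed.
4. Check register completeness for decliners over the recruitment period. If it is poor, report both figures with that limitation and do not present either as definitive.

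The cost is protocol wording, a tabulation of fields already on the registers and interview forms, and the completeness check, which is the main effort. Recruitment, the questionnaires and the sample size do not change.

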Economic evaluation methods will include document reviews and exit interviews with individuals accessing HIV testing services.

In the **two secondary distribution models**, the study will explore factors associated with successful secondary distribution of test kits. Specific objectives are to measure:

9. Factors associated with acceptance of HIVST for secondary distribution to index patients, acceptance being evidenced by accepting an HIVST kit(s) for onward secondary distribution.
10. Factors associated with the successful secondary distribution of HIVST to the sexual partners (the intended users of the secondary distribution HIVST kits) of index patients, as evidenced by the proportion of index patients who report that their primary partners used the HIVST kit within 1 month of distribution
11. The proportion of intended users of the secondary distribution HIVST kit who report having accessed confirmatory testing, or HIV prevention or care services within 3 months of distribution
12. User experiences and factors affecting the potential for social harms

To meet these objectives, we will administer a quantitative exit interview after the clinical consultation to determine the proportion of individuals who accepted an offer of an HIVST for secondary distribution and factors associated with acceptability of an offer of a secondary distribution HIVST (objective 9). For individuals who accepted the offer of a secondary distribution HIVST, we will conduct a follow-up questionnaire approximately 1-month after the initial exit interview to measure use of the HIVST kit (objective 10) and will follow-up their partner approximately 3-months after distribution to measure linkage to confirmatory testing, HIV care or prevention services (objective 11). To complement the quantitative data, a purposive sample of individuals participating in the exit interview will be followed-up at three-time points as part of a qualitative cohort, with IDI conducted each time point to understand

user experiences, factors influencing secondary distribution of an HIVST, and social harms (objective 12).

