### **7.4 Cost data**

Cost data will be analysed separately by the economics team in STATA 14. Costs will be descriptively categorised into direct and indirect costs. To assess the economic burden HIVST,

we will compare sum of patients' direct non-medical and indirect costs with the household per capita expenditure. We will use a multivariable Tobit regression model to determine cost predictors.

Among individuals participating in the follow-up survey, we will describe reported use of the HIVST and investigate factors associated with reporting use of the secondary distribution HIVST. We will also describe linkage to ART or voluntary medical male circumcision, and time to linkage to care. Linkage data will primarily rely on reported use by the index individual, but we also aim to describe this among the intended users if consent is provided to follow-up partners and partners consent to participate in the study.

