Use_HIVST 3	Did you give your partner an HIV self-test kit that you collected on his behalf?	No; Yes	0; 1
Use_HIVST 3a	If no, why did you not give the HIVST to your partner?	I lost the kit; my partner already knows his/her HIV positive status; I feared my partner would get angry; my partner has been away from the time I collected the test kit; my partner and I are no longer in partnership; other (Specify); refuse to respond	1; 2; 3; 4; 5; 6; 7
Use_HIVST 4	Did your partner use the HIV self-test that you gave him?	Yes – I was present when he used the self-test; Yes – I was told that the self-test kit was used; No- he did not use the self-test kit; I Don't know	1; 2; 3; 4
Use_HIVST 5	What was the date that your partner used	Year; month; day	

	the HIV self-test kit?		
Use_HIVST 6	When your partner used the self-test, did you also use a self-test at the same time?	Yes (Couple testing); No; Don't know	1; 2; 3
Use_HIVST 7	What were the results of your self-test?	HIV-positive; HIV-negative; Indeterminate; Don't know; Refused to answer	1; 2; 3; 4; 5; 6
Use_HIVST 8	Do you know the results of your partner's HIV test?	No; Yes; Don't know; Refused to answer	1; 2; 3; 5
Use_HIVST 9	What was your partner's test result?  Interviewer: Remind participant that they do not have to answer this question if uncomfortable. If she says that she knows but doesn't want to share – this is code 99. If the person tested but did not share the result with them so they don't know, this is code 98	HIV-positive; HIV-negative; Indeterminate; Don't know; Refused to answer	1; 2; 3; 4; 5
Use_HIVST 10	Did your partner go to a clinic or health facility in order to confirm the result that was obtained from the self-test (confirmatory testing)?	No; Yes; Don't know	0; 1; 2
Use_HIVST 11	Did your partner go to a clinic or health facility for HIV care?	No; Yes; Don't know	0; 1; 2
Use_HIVST 122	Is your partner currently in ART care?	No; Yes; Don't know	0; 1; 2
Use_HIVST 13	Did your partner go to the clinic or health facility for HIV prevention services?	No; Yes; Don't know	0; 1; 2
Use_HIVST 14	What HIV prevention services did they go for?	VMMC; to collect condoms; other (specify)	0; 1; 2

Social Harms/benefits Screening at follow-up visit			
Variable Name	Question	Options	Option Codes

SHS_Fu_1	When you gave your partner the HIV test kits, did you explain that it is for HIV testing?	Yes; No; Don't know	1; 2; 3

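### The index follow-up interview is timed in two different ways and the primary outcome has no time window, so an interview held early but within the rules counts later partner use as non-use

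*Protocol*

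**What the plan says.** Section 4.3.2 and the consent step in section 5.2 both place the index interview inside the first month. In 5.2, acceptors are "asked for their consent to be followed-up as they come back for their clinical appointment or at home within 1-month" of the exit interview. The following paragraph of 5.2 gives a target date instead: "Approximately one-month after the offer of HIVST for secondary distribution, RAs will follow-up cohort participants". The Summary also describes a questionnaire at about one month.

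Objective 10 in the Summary is evidenced by index patients reporting that "their primary partners used the HIVST kit within 1 month of distribution"; section 2.2 softens this to approximately one month. The sample size in section 5.4 assumes 60% and 40% reported use at the one-month follow-up.

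The primary outcome in section 4.3.2 is the proportion of "index patients who accepted an offer of secondary distribution HIVST kit(s) who report that their sexual partner(s) used the HIVST kit", with no time limit. Secondary outcome 2 in the same list does have a one-month limit.

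On who is analysed, section 7.4 says: "Among individuals participating in the follow-up survey, we will describe reported use of the HIVST". Section 5.4 expects up to 30% of acceptors to be lost.

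The index follow-up questionnaire in Appendix 3 asks when the kit was collected (Use_HIVST 1) and "What was the date that your partner used" it (Use_HIVST 5).

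**The concern.** *Within* one month and *about* one month are different designs. Under the first, an interview in week three is on protocol but cannot show whether the partner used the kit by day 30. If the partner tests the following week, the index patient has already been scored as reporting no use. Nobody is asked again, because the next planned contact, at about three months, is with the partner, and only where the index patient has already reported use. The loss of information is built into data collection.

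Two things are at stake. The first is the headline proportion, which falls as interviews come earlier. The second is the comparison by factor (knowledge of partner status in the ANC cohort, disclosure in the HIV-positive cohort), which could be distorted if one level of the factor tends to be interviewed earlier than the other.

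**Working it through.** **1. The timing statements side by side**

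| Place | Timing |
|---|---|
| 4.3.2 text; 5.2 consent step | interview within one month |
| Summary; 5.2 next paragraph | interview about one month after |
| Summary, objective 10 | use within one month |
| 2.2, objective 10 | use within about one month |
| 5.4 | use at the one-month follow-up |
| 4.3.2, primary outcome | none |

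No earliest or latest interview day is given.

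**2. The plan's own figure**

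Inputs from 5.4: 60% v 40%, at least 80% power, 0.05 level (taken as two-sided). With k the ratio of group sizes and p̄ the weighted mean proportion, the smaller group needs

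n = [1.96·√((1+1/k)·p̄(1−p̄)) + 0.842·√(p₁q₁ + p₂q₂/k)]² / (p₁−p₂)².

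- k = 1: [1.96·√0.5 + 0.842·√0.48]² / 0.04 gives 97 per group, 194 in total.
- k = 4: 60 in the smaller group, 300 in total.

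The factor split is not stated, so 300 cannot be pinned down. It does give at least 80% power for any factor prevalence from 20% to 80%. For loss, 300/0.7 = 429, rounded up to about 450, and 450 × 0.7 = 315. The sample size stands, but it rests on 60% and 40% being read at one month.

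**3. What an early interview does to the level**

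Assumption, not in the documents: use accrues at a constant rate and reaches the planned 60% and 40% at day 30. Then reported use at day d is P(d) = 1 − (1 − P₃₀)^(d/30). At day 21, 1 − 0.4^0.7 = 0.473 and 1 − 0.6^0.7 = 0.301.

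| Everyone interviewed at | Factor present | Factor absent | Power, 315 evaluable, equal split |
|---|---|---|---|
| day 14 | 34.8% | 21.2% | 77% |
| day 21 | 47.3% | 30.1% | 89% |
| day 28 | 57.5% | 37.9% | 94% |
| day 30 | 60.0% | 40.0% | 95% |

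The day-14 row shows the range only; nothing in the protocol says interviews will be that early. In every row timing is the same for both groups, so the level falls and some power goes, but no false association arises.

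**4. When an association would be distorted**

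This needs a further assumption, that interview dates differ by the factor. Take identical behaviour, 50% use at day 30 in both groups, 315 evaluable and an equal split.

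- Day 30 v day 21: 50.0% v 1 − 0.5^0.7 = 38.4%. OR = 1/(0.384/0.616) = 1.60, with a false positive in about 54% of studies.
- Day 28 v day 21: 47.6% v 38.4%. OR 1.46, about 38%.

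**5. What the recorded dates can repair**

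- Interview on or after day 30: use by day 30 follows from Use_HIVST 1 and Use_HIVST 5.
- Interview before day 30, use reported: already counts as use.
- Interview before day 30, no use reported: status at day 30 is unknown.

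Only the third case is beyond repair.

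**6. Loss to follow-up**

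With the full 30% lost and, by assumption, 50% use among those seen, counting every lost acceptor as a non-user gives 0.7 × 0.50 = 35% of all acceptors.

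**The case against.** The best defence is that the protocol means one month throughout. Section 5.2 sets that target and traces people who miss their appointment by phone or home visit, with up to three attempts. Objective 10 and sections 5.4 and 7.3 also refer to one month. On this view the missing window in 4.3.2 is a gap in a list. The ART visit intervals named in the costing form start at monthly, so very early appointments are not evident there. The cohorts are analysed separately with adjustment for site, which takes up some variation in appointment spacing.

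Much of this is right, and it rules out several stronger readings.

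- A reader might infer that the outcome is taken at whatever date the patient happens to return. The one-month target and the tracing contradict that.
- A reader might infer that timing alone could produce a difference as large as the planned 20 points. That needs whole groups interviewed at very different times, for which the documents give no evidence. Reported use would depend on timing as well as on the factors, not instead of them.
- A reader might infer that late interviews give extra time for use. The recorded dates allow that to be corrected.
- A reader might infer that the protocol is deficient for lacking weighting or other missing-data methods. Those commonly sit in an analysis plan, which is not shown here.

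What the defence does not answer is the compliant early interview. Tracing is aimed at people who do not come back on their appointment day, so someone whose appointment falls before one month may be interviewed then, exactly as the consent step allows.

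**Conclusion.** The point holds as an inconsistency with a real, one-directional consequence. The interview timing is worded in two ways, the primary outcome has no window, and one of the wordings permits interviews that misclassify later use as non-use. The effect is to lower the reported proportion. Under the constant-rate assumption, 60% reads as 47% if everyone is seen at day 21 and as 57.5% at day 28. Actual interview dates are not known from the protocol, so the true size could be small.

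Bias in the associations is possible but conditional on timing that differs by factor, which the documents do not show. The sample size is not in question. Loss to follow-up is secondary: the outcome is defined over acceptors and described among those re-interviewed, and the reported figure should say which it is. The timing should be settled before follow-up interviews start, because use after an early interview cannot be recovered.

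**What to change.** - **Section 4.3.2, primary outcome.** Define it as partner use within 30 days of kit collection, derived from Use_HIVST 1 and Use_HIVST 5, and align objective 10 with it.
- **Summary, 4.3.2 text and both places in 5.2.** State one interview window that opens no earlier than day 30, for example day 30 to 45. Where the appointment falls earlier, use the phone or home contact that 5.2 already provides for.
- **Analysis.** Treat any interview before day 30 without reported use as censored at that date, not as non-use.
- **Loss.** Label the proportion as among index patients followed up, and report beside it the figure that counts all lost acceptors as non-users.

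The cost is a few changes of wording, and some early clinic interviews that become a call or home visit. The use date is reported by the index patient and will sometimes be unknown, so a short rule for that case is needed; it can go in the analysis plan.
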